### **5.5.2 Biomarker Methodology**

In Part A and Part B, PK blood samples to determine ubrogepant plasma concentrations will be collected at 0 hour (predose) and 0.25, 0.5, 1, 1.5, 2, 3, 4, 5, 6, 8, 12, 14, and 24 hours postdose on Days 1 and 12. These samples will also be used for the determination of biomarker (CGRP) concentrations. [redacted]  
[redacted]

[redacted]. Plasma and [redacted] of CGRP will be determined using a qualified ELISA assay.

## 5.6 Data Handling and Storage

A source data file from [REDACTED] will be transferred to Data Management via secure File Transfer Protocol (sFTP). Data Management will use the data for reconciliation against case report form (CRF) data and general cleaning.

Data Management shall provide the data file to Statistical Programming who will add the data to the [REDACTED] software for the calculation of PK parameters. Once the [REDACTED] is created, Statistical Programming will notify the Allergan Clinical Pharmacology representative via email and transfer it to the relevant group via a shared study-specific repository, in the [REDACTED].

Pharmacokinetic analysis and statistical analysis of pharmacokinetic data will be performed using [REDACTED] or other appropriate software.

Unless otherwise specified in subsequent sections, these general data handling instructions will be followed:

- All measured data will be used in analysis initially unless it may be excluded in accordance to regulatory guidances. Measured data not used and the reasons for its exclusion from the final analysis will be documented in the clinical study report (CSR).
- The actual sampling times will be used in the calculations of PK parameter values, nominal sample times will be used in the calculation of descriptive statistics.
- All postdose time points for which no sample is collected will be treated as missing. No value will be imputed for these missing values.
- Concentration data below the lower limit of quantitation (BLQ) will be defaulted to 0.00.

A data file (‘.xpt’ or ‘.xls’ format) containing PK parameter values will be generated by the Clinical Pharmacology representative and added to the shared study-specific repository for retrieval by Statistical Programming and for archival. If necessary, a document defining the content and CDISC parameter names will also be provided. Other files necessary to reproduce the analysis of PK parameter values, e.g., the WinNonlin Project file, will be archived in PKS or another appropriate study-specific repository.

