8.8. Biomarkers and Other Assessments

Measurement of CGRP concentrations in plasma [REDACTED] will be attempted from the PK samples at the timepoints specified in Sections 8.5.1 and 8.5.2. These samples will be collected, processed, and shipped as described in Sections 8.5.1 and 8.5.2 above.

Biomarker blood samples should be drawn at the nominal times specified above, relative to the dosing time, and the actual time of the blood draw must be recorded in the source documents and eCRFs. Samples taken more than ± 5 minutes from the nominal time will be noted as protocol deviations, and the reason for deviation must be recorded in the source documents and eCRFs. Predose samples must be drawn within 30 minutes of the dosing time.

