### **3 Introduction**

The data analyses outlined in this document are to support clinical study 3110-108-002. In this study, measurements will be made for ubrogepant and CGRP concentrations in plasma [REDACTED]. This data analysis plan (DAP) outlines how data analyses of these measurements will be conducted. Additional analysis may be conducted, if necessary. Safety analyses are described separately in the Statistical Analysis Plan.

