## 6.2 Biomarkers

The percent change from baseline in plasma CGRP levels will be calculated using Excel 2016 (or newer) and will be presented by study intervention and nominal timepoint for each part of the study for the PK3 population. [REDACTED]

[REDACTED]

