### **PK3 Population**

For each part of the study, individual values and descriptive statistics will be reported for the plasma CGRP concentrations at each nominal time point for all participants in the PK3 population. Changes at postdose from baseline by study intervention will be reported for the plasma CGRP concentrations at each nominal time point by study part for all participants in the PK3 population.

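### On the visible text, CGRP values below the quantitation limit are set to zero, so percent change from baseline is undefined or forced to −100% and its summary is biased downward whenever such values occur

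*SAP*

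**What the plan says.** The SAP's introduction names ubrogepant and CGRP concentrations as the measurements and says: "This data analysis plan (DAP) outlines how data analyses of these measurements will be conducted". SAP 5.6 opens its list of rules with "Unless otherwise specified in subsequent sections, these general data handling instructions will be followed", and one of those rules is "Concentration data below the lower limit of quantitation (BLQ) will be defaulted to 0.00".

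For CGRP, SAP 6.2 states: "The percent change from baseline in plasma CGRP levels will be calculated using Excel 2016". The PK3 part of SAP 7.1 adds that "individual values and descriptive statistics will be reported for the plasma CGRP concentrations at each nominal time point" and that "Changes at postdose from baseline by study intervention will be reported for the plasma CGRP concentrations". Neither section, as far as it can be read, gives a separate rule for CGRP values below the limit. Redacted text follows SAP 6.2.

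The PK3 population (SAP 5.2) needs only one CGRP measurement per participant, so a participant with a BLQ baseline stays in it. Protocol 9.4.1 also treats BLQ values as zero, but only for PK calculations. Protocol 8.8 says that CGRP measurement "will be attempted from the PK samples at the timepoints specified". No LLOQ and no expected BLQ rate for CGRP is visible in either document.

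**The concern.** Zero is a workable value for a drug before its first dose. It is a poor one for an endogenous peptide summarised as percent change, because the baseline is the denominator.

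The two consequences do not cancel. A participant who falls from just above the limit to just below it is kept and scored at the largest possible fall. A participant who rises from just below to just above has a zero baseline and drops out of the calculation. Falls across the limit are exaggerated and rises across it are lost.

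At stake is the reading of the CGRP tables. The study drugs act on CGRP or its receptor, so an artificial fall would look plausible. The visible plan does not ask for BLQ counts beside the summaries that would warn the reader.

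**Working it through.** The plan states no CGRP effect, LLOQ or BLQ rate, so there is no figure to reproduce. The check is algebra, then a simulation on stated assumptions.

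**Algebra.** The SAP does not print the formula; the standard one is 100 × (postdose − baseline) / baseline.

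- BLQ baseline, set to 0: the denominator is 0 and there is no value, whether or not the postdose value is measurable.
- Measurable baseline *b*, BLQ postdose set to 0: 100 × (0 − *b*) / *b* = −100%.
- What that second case really means: if *b* = k × LLOQ, a postdose value below the LLOQ implies a change between −100% and 100 × (1/k − 1). For k = 1.25, 2, 5 and 10 the upper end is −20%, −50%, −80% and −90%. The rule records −100% each time.

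Every defined percent change is thus at or below its true value. In addition, the dropped participants are those with low baselines, who tend to show the larger relative rises.

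**Simulation, no true change.** Assumptions: lognormal values, between-participant CV 50%, within-participant CV 20% to 50%, LLOQ placed to give the stated BLQ rate, 1,000,000 baseline/postdose pairs per setting. The uncensored arithmetic mean percent change is itself above zero: for independent lognormal errors it equals 100 × CV², that is 100 × 0.2² = +4% and 100 × 0.5² = +25%. Undefined baselines are the BLQ rate times the 20 participants in each part.

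| BLQ rate | Undefined, of 20 | Within-CV 20%: uncensored → rule (shift) | Within-CV 50%: uncensored → rule (shift) |
|---|---|---|---|
| 5% | 1 | +4% → about +1% (−2.6 points) | +25% → about +17% (−7.7 points) |
| 20% | 4 | +4% → about −4% (−8.3 points) | +25% → about +2% (−23.2 points) |
| 50% | 10 | +4% → about −15% (−19.1 points) | +25% → about −24% (−49.0 points) |

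The true median change is 0. Under the rule it is −2.7% to −10.9% at 20% BLQ and −6.3% to −27.7% at 50%. The share of defined values at exactly −100% is 8–14% and 18–33% respectively.

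**Where the shift comes from.** With log SDs of 0.5 between and 0.3 within participants and 30% BLQ, the true mean is +9.5%. It is +0.7% among participants with a measurable baseline, and −8.3% under the rule. Dropping low baselines accounts for 9.5 − 0.7 = 8.8 points and the forced −100% values for 0.7 + 8.3 = 9.0 points.

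**With a true change** (same log SDs, baseline BLQ 5%, 10%, 30%, 50%):

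- True postdose/baseline ratio 0.7: true mean percent change about −23.4%; the rule gives −30.9%, −35.7%, −49.7%, −60.2%.
- Ratio 1.5: true mean about +64%; the rule gives +60.6%, +58.2%, +49.2%, +40.2%.

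**Absolute change** (in units of the median baseline, same settings) behaves differently, because a zero baseline stays in and overstates that participant's change:

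- Ratio 1.5: true +0.59; the rule gives +0.60 to +0.74, an upward bias.
- Ratio 1.0: net bias about 0.
- Ratio 0.7: true −0.36; the rule gives −0.38 to −0.46, a downward bias.

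**The case against.** The strongest reply has four parts.

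*The plan may already deal with it.* Zero is a default that later sections may override, and redacted text follows SAP 6.2, where a CGRP rule would sit. This stands as a condition: the point is made on the visible text, and the sponsor may only need to confirm the rule.

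*BLQ values may not occur.* The wording in protocol 8.8 makes values near the limit foreseeable but does not establish them; part of that sentence is redacted and no reason is given for it. With no BLQ values there is no bias. This also stands.

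*The shift is not the same as a false fall.* A reader might infer from the shifts that the tables would show a CGRP reduction where there is none. At 20% BLQ the resulting means are only about −4% to +2%, because the uncensored arithmetic mean starts above zero; the medians, at about −3% to −11%, show a modest fall. A clear false fall in the mean appears at about 50% BLQ, and nothing in the documents indicates such a rate.

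*The consequence is limited.* The visible CGRP analyses are descriptive, and the 80–125% conclusion in SAP 7.2 uses only ubrogepant Cmax and AUC. Individual CGRP values are reported, so a careful reader could find the zeros. That limits the harm but does not correct the summary.

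A reader might also infer that every CGRP summary is biased downward; the absolute-change results show otherwise. Another tempting step is to require the Day 1 predose sample as the baseline, since the visible text does not say which predose sample is meant. That is a separate question. A Day 12 baseline would isolate the effect of adding ubrogepant, a Day 1 baseline would include the antibody, and the choice depends on an objective that cannot be seen.

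**Conclusion.** The point holds on the visible text and conditionally. A drug-concentration convention is applied to a biomarker, further than protocol 9.4.1 takes it. Whenever BLQ values occur, some percent changes are undefined, others are fixed at −100%, and the percent-change summary is too low.

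Under the assumed CVs and no true change, the mean percent change is lowered by about 3 to 8 points at 5% BLQ, 8 to 23 at 20% and 19 to 49 at 50%. Those figures rest on the lognormal model and on CVs and BLQ rates that the documents do not give. The effect is confined to the CGRP tables; the primary drug-interaction conclusion does not depend on it. It deserves correction because the rule gives a wrong answer when followed and is easy to change.

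**What to change.** Unless redacted text already covers this:

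1. In SAP 5.6, limit the zero rule to ubrogepant PK, in line with protocol 9.4.1.
2. In SAP 6.2 and 7.1, analyse CGRP change as a log ratio, with BLQ values at baseline or postdose treated as left-censored at the LLOQ.
3. Use a fixed substitution such as LLOQ/2 only as a sensitivity check. With no true change it returns a ratio of 1 simply because baseline and postdose are affected alike. With a true change it is biased: across the settings run, a true ratio of 1.5 reads about 1.50 to 1.59 and a true 0.7 about 0.66 to 0.76.
4. Report the number and percent of BLQ values at each time point.

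The cost is a few sentences in the SAP, slightly more programming than a spreadsheet percent change, and a short explanation of the censored analysis in the report. No new samples or visits are needed.

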## 6 Data Analysis

### 6.1 Pharmacokinetics

The following pharmacokinetic parameters for ubrogepant determined from plasma concentration data for each part of the study will be calculated using noncompartmental analysis:

AUC 0-t	Area under the plasma concentration-time curve from time 0 to t hours post-dose, calculated by the linear-log trapezoidal rule
AUC 0-∞	Area under the plasma concentration-time curve from time 0 to infinity, as calculated by Phoenix WinNonlin (AUC 0-∞ ). AUC 0-∞ values will be calculated and reported for all participants, however values will only be included in the summary statistics and statistical analysis if the % extrapolated area (AUC%) is ≤ 20%.
AUC%	Percent of AUC extrapolated from the last measurable concentration to infinity: [AUC% = (((AUC 0-∞ - AUC 0-t )/AUC 0-∞ ) * 100)]
C max	Maximal observed plasma concentration
CL/F	Apparent oral clearance is the oral dose divided by AUC 0-∞
λ z	Apparent terminal-phase rate constant, determined by performing a regression analysis on the terminal linear phase of semi-logarithmic plots of individual concentration-time data using a minimum of three concentration-time points in the elimination phase excluding C max . λ z will be considered to be valid if r  > 0.80. The values included in the regression analyses will be determined by WinNonlin and will be reviewed and revised as necessary by the Clinical Pharmacologist.
T max	Time corresponding to maximal plasma concentration
T ½	Apparent terminal-phase half-life, calculated as 0.693/λ z
V z /F	Apparent volume of distribution during the terminal phase after extravascular administration

If the extrapolated AUC is > 20%, the AUC0-∞, CL/F, and Vz/F values will be listed by participant but excluded from descriptive statistics.

The PK parameter values will be reported up to at least 2 decimal places. [REDACTED]

[REDACTED]

[REDACTED]

## 6.2 Biomarkers

The percent change from baseline in plasma CGRP levels will be calculated using Excel 2016 (or newer) and will be presented by study intervention and nominal timepoint for each part of the study for the PK3 population. [REDACTED]

[REDACTED]

## 7 Data Summarization and Statistical Analysis

### 7.1 Data Summarization

#### PK1 Population

Descriptive statistics (arithmetic mean, standard deviation, relative standard deviation, maximum, minimum) will be reported for the plasma concentrations of ubrogepant at each nominal time point for all participants in the PK1 Population by study part and by study intervention. Descriptive statistics (arithmetic mean, standard deviation, relative standard deviation, maximum, median, minimum) will be calculated for ubrogepant PK parameters for each study part by study intervention for all participants in the PK1 Population. Additionally, the geometric mean will be reported for ubrogepant  $C_{max}$ ,  $AUC_{0-t}$ ,  $AUC_{0-\infty}$ ,  $CL/F$ , and  $V_z/F$  parameters.

[REDACTED]

### **PK3 Population**

For each part of the study, individual values and descriptive statistics will be reported for the plasma CGRP concentrations at each nominal time point for all participants in the PK3 population. Changes at postdose from baseline by study intervention will be reported for the plasma CGRP concentrations at each nominal time point by study part for all participants in the PK3 population.

## **7.2 Statistical Analysis**

Plasma PK parameters ( $C_{max}$ ,  $AUC_{0-t}$ , and  $AUC_{0-\infty}$ ) for ubrogepant will be compared using a linear mixed-effects model with study intervention as fixed effect and participant as a random effect in each part of the study for the PK1 population. Statistical analysis will be based on log-transformed values for the  $C_{max}$  and AUC parameters of ubrogepant. For each study part, the 2-sided 90% CI will be constructed for the ratio of least squares geometric means of  $C_{max}$ ,  $AUC_{0-t}$ , and  $AUC_{0-\infty}$  of ubrogepant in combination with CGRP MAB (Test, Day 12) versus ubrogepant alone (Reference, Day 1). No effect of co-administration with CGRP MABs on the PK of ubrogepant will be concluded if the 90% CIs for the ratios of ubrogepant PK parameters for test study intervention versus reference study intervention are within the limits of 80% to 125%.

## **8 Presentation of Final Results**

Presentation of data will be performed using the software described in Section 5.4.

- Ratios, coefficient of variation, and confidence intervals will be presented as percentages.
- Percentages will be presented to 2 decimal places.
- Descriptive statistics presented in summary tables in the study report will be presented to a number of decimal places (at least 2) that is consistent with the data from which the statistics were derived.
- Participants will be identified in the listings using their participant number.

All data used, and results will be presented in data tables and listings.

**9                    Changes to Analysis Plan**

None

